1.2 Study objectives, endpoints and estimands

Objective(s)	Endpoint(s)
Primary objective(s)	Endpoint(s) for primary objective(s)

To assess the effect on LDL-C of implementation of an LDL-C management care pathway that includes initiation of inclisiran in participants with a recent hospitalization (in-patient/out-patient) for an ACS with LDL-C ≥ 70 mg/dL despite receiving statin therapy compared to usual care without inclisiran at Day 330	
Percent change from baseline in LDL-CAchieving LDL-C < 70 mg/dL (yes, no)
Secondary objective(s)	Endpoint(s) for secondary objective(s)

To assess (1) the absolute change from baseline in LDL-C level by visit, and (2) average of percent and absolute changes from baseline in LDL-C levels to each post-baseline visit, in the inclisiran + usual care group compared to usual care group at Day 330To assess the proportion of participants reaching pre-specified LDL-C targets in the inclisiran + usual care group compared to usual care group at Day 330To assess plasma lipoproteins and triglycerides in the inclisiran + usual care group compared to usual care group at Day 330To assess changes in and adherence to background lipid-lowering therapy in the inclisiran + usual care group compared to usual care group at Day 330	
Absolute change from baseline in LDL-CAverage percent change from baseline in LDL-C levels to each post-baseline visitAverage absolute change from baseline in LDL-C levels to each post-baseline visitAchieving $\geq 50\%$ reduction from baseline in LDL-C (yes, no)Achieving LDL-C < 100 mg/dL (yes, no) (among the subset of participants with LDL-C ≥ 100 mg/dL at baseline)Achieving LDL-C < 55 mg/dL (yes, no)Percent change and absolute change from baseline in apoBPercent change and absolute change from baseline in VLDLPercent change and absolute change from baseline in non-HDL-CPercent change and absolute change from baseline in total cholesterolPercent change and absolute change from baseline in Lp(a)Percent change and absolute change from baseline in HDL-CPercent change and absolute change from baseline in triglyceridesIntensity of lipid lowering therapy (decrease in dose, no change in dose, increase in dose)Proportion of days covered (total number of days on either statin, ezetimibe, or PCSK9 inhibiting monoclonal antibody therapies divided by total number of study days)

Objective(s)	Endpoint(s)

• To assess overall safety and tolerability of inclisiran	
• Discontinuation of statin therapy (i.e., no statin use \geq 30 days before the end-of-study visit) (yes, no)• Adverse events
Exploratory objective(s)	Endpoint(s) for exploratory objective(s)

• To assess major adverse cardiovascular events (MACE) (investigator determination) in the inclisiran + usual care group compared to usual care group at Day 330	
• Cardiovascular death (yes, no)• Non-fatal MI (yes, no)• Resuscitated cardiac arrest (yes, no)• Non-fatal ischemic stroke (yes, no)• Composite MACE (cardiovascular death, non-fatal MI, resuscitated cardiac arrest, or non-fatal ischemic stroke) (yes, no)

Note that endpoints identified as “absolute” change from baseline correspond to values that are calculated as a change from baseline (post-baseline value minus baseline value).

1.2.1 Primary estimand(s)

The estimand is the precise description of the treatment effect and reflects strategies to address events occurring during the trial conduct which could impact the interpretation of the trial results (e.g., premature discontinuation of treatment).

The primary clinical question of interest in this study is to evaluate the effect on LDL-C of implementation of an LDL-C management care pathway with inclisiran versus usual care in participants who are discharged after an ACS on statin therapy or have documented statin intolerance and do not have their LDL-C at the target level. The justification for the primary estimand is that it will evaluate the LDL-C lowering effect of inclisiran on both the percent change in LDL-C and the achievement of the target LDL-C (<70 mg/dL) compared to a usual care of implementation pathway in participants following a recent ACS, including potential changes in concomitant therapy. Further details can be found in Section 12 of the protocol.

Primary estimand 1: The primary analysis of primary efficacy variable 1 (percent change from baseline in LDL-C) to address the primary objective will be based on the following estimand:

- Population: Defined through appropriate inclusion/exclusion criteria to reflect the targeted population
- Variable: Percent change from baseline in LDL-C [The primary analysis time point is at Day 330.]
- Treatment: Inclisiran + usual care or usual care
- Remaining intercurrent events: 1. Potential use of inclisiran by participants in the usual care group. This intercurrent event will be ignored in the analysis, as the design of the trial allows for participants in the usual care group to potentially use inclisiran. 2. Discontinuation of study treatment. This intercurrent event will be ignored in the analysis. 3. Use of prohibited medication (monoclonal antibodies directed against PCSK9) in the inclisiran + usual care group. This intercurrent event will be ignored in the analysis.
- Summary measure: Least-squares mean difference between inclisiran + usual care group and usual care group

Primary estimand 2: The primary analysis of primary efficacy variable 2 (achieving LDL-C < 70 mg/dL) to address the primary objective will be based on the following estimand:

- Population: Defined through appropriate inclusion/exclusion criteria to reflect the targeted population
- Variable: Achieving LDL-C < 70 mg/dL (yes, no) [The primary analysis time point is at Day 330.]
- Treatment: Inclisiran + usual care or usual care
- Remaining intercurrent events: 1. Potential use of inclisiran by participants in the usual care group. This intercurrent event will be ignored in the analysis, as the design of the trial allows for participants in the usual care group to potentially use inclisiran. 2. Discontinuation of study treatment. This intercurrent event will be ignored in the analysis. 3. Use of prohibited medication (monoclonal antibodies directed against PCSK9) in the inclisiran + usual care group. This intercurrent event will be ignored in the analysis.
- Summary measure: Odds ratio of inclisiran + usual care to usual care for achieving LDL-C < 70 mg/dL

1.2.2 Secondary estimand(s)

Not applicable.

2 Statistical methods

This section contains information that will be used to draft CSR Section 9.7 on statistical analysis.

2.1 Data analysis general information

It is planned that the data from all centers that participate in this protocol will be combined, so that an adequate number of participants will be available for analysis.

Any data analysis carried out independently by the investigator should be submitted to Novartis before publication or presentation.

The analysis will be performed at the end of the trial, after the clinical database is locked.

Unless otherwise specified, all statistical tests will be conducted against a two-sided alternative hypothesis, employing a significance level of 0.05.

Efficacy, safety, and other data will be summarized. For continuous variables, summary statistics (mean, standard deviation, median, 25th and 75th percentiles, minimum, and maximum) at each time point and for change from baseline to each time point will be reported by treatment group. For discrete variables, frequency counts and percentages at each time point will be reported by treatment group.

LDL-C values, lipid parameters, and laboratory units

Any statistical analysis involving LDL-C will be based on calculated LDL-C values as provided by the central laboratory. For the remainder of this SAP and the corresponding output shells, the abbreviated term “LDL-C” refers to calculated LDL-C.

Tabular summaries, listings, and figures of lipid parameters, creatinine, and fasting glucose will be provided in US conventional units. Select analyses of these parameters will be provided in SI units as well. All other laboratory parameters will be reported in SI units. Both US conventional and SI units will be included in SDTM and ADaM datasets as applicable per laboratory parameter. The lipid parameters include the following, with US and SI units as applicable in this study:

1. LDL Cholesterol (mg/dL, mmol/L)
2. Total Cholesterol (mg/dL, mmol/L)
3. HDL Cholesterol (mg/dL, mmol/L)
4. Non-HDL Cholesterol (mg/dL, mmol/L)
5. VLDL Cholesterol (mg/dL, mmol/L)
6. Triglycerides (mg/dL, mmol/L)
7. Apolipoprotein B (mg/dL)

8. Lipoprotein(a) (nmol/L)

Due to differences in measurement techniques as well as molecular differences between individuals, a standardized conversion factor is not available to convert Lipoprotein(a) values from standard to US conventional units. Therefore, Lipoprotein(a) results will only be reported in nmol/L.

2.1.1 General definitions

Study treatment

The following are the investigational treatments:

- Inclisiran (KJX839), 284 mg, 1.5 ml liquid in a single-use prefilled syringe (PFS) for s.c. administration plus usual care
- Usual care alone

The following treatment labels will be used for all tables, listings and figures:

- Inclisiran + Usual Care
- Usual Care

Study treatment start and end date

Study treatment start date is defined as the first date when a non-zero dose of study drug is administered for the inclisiran + usual care group. If a participant, who is randomized to the inclisiran + usual care group, does not take any study drug then treatment start date will be the randomization date.

For the usual care alone group the study treatment start date will be the randomization date.

“Day 1” will be used to identify study treatment start date for both treatments.

Study treatment end date is defined as the treatment phase completion date recorded on the “Treatment Disposition” CRF for inclisiran + usual care participants. For the usual care alone group, the study treatment end date is the last recorded contact/participation date in the database.

Study start and end date

Study start date is defined as the first date when a non-zero dose of study drug is administered for the inclisiran + usual care group. If a participant, who is randomized to the inclisiran + usual care group, does not take any study drug then study start date will be the randomization date.

For the usual care alone group the study start date will be the randomization date.

Study end date is defined as the date of last recorded contact/participation date in the database.

Duration of exposure to inclisiran

For the inclisiran + usual care group, duration of exposure to inclisiran (in days) is defined as the number of days from Day 1 to the study *treatment* end date. Duration of exposure will not be defined for the usual care alone group.

Planned and actual treatment definitions

The following definitions will be used for planned and actual treatment.

Table 2-1 Planned and Actual Treatment Definitions

Randomized Treatment Group	Inclisiran Use Scenario During Study (Inclisiran Use Recorded as Study Treatment or Concomitant Medication)	Planned Treatment	Actual Treatment
Inclisiran + Usual Care	Received at least one dose of inclisiran	Inclisiran + Usual Care	Inclisiran + Usual Care
Inclisiran + Usual Care	Never received inclisiran	Inclisiran + Usual Care	Usual Care
Usual Care	Received at least one dose of inclisiran	Usual Care	Inclisiran + Usual Care
Usual Care	Never received inclisiran	Usual Care	Usual Care

Study day

Study day will be calculated as (event date – study treatment start date + 1 day) for events that occurred on or after study treatment start date (e.g., visit, lab samples, AEs). For events prior to study treatment start date (e.g., time of diagnosis), study day will be negative and calculated as (event date – study treatment start date). Note that study treatment start date is study Day 1 and the day before study drug start date is study Day -1 (i.e., no study Day 0).

Screening, baseline and post-baseline definitions

A screening value refers to the last available measurement from the set of nominal Screening/Visit 1 records irrespective of collection date being before or after start of study treatment, and any unscheduled visit data collected before (<) study Day 1.

In general, a baseline value refers to the last measurement available prior to administration of the first dose of study treatment (before or on study Day 1). A post-baseline value refers to a measurement taken after the first dose of study treatment (after study Day 1).

Lost to follow up

Participants whose study completion status is unclear because they fail to appear for study visits without stating an intention to withdraw.

On-treatment period

The period where the participants are exposed to the study treatment or usual care. For this study the treatment phase consists of 330 days.

Study Completer

Completers are defined as a participant who has a Subject Status of ‘completed’ on the Study Completion/Exit CRF page.

Analysis Visit Windows

The following analysis windows will be used for efficacy and safety analyses.

Table 2-2 Analysis Windows for Each Scheduled Visit

Analysis Visit	Target Study Day*	Analysis Window	
		From	To
Baseline	1		Before randomization/First Study Treatment
Day 90	91	1	180
Day 270	271	181	300
Day 330	331	301	375

* Study Day 1 is being used to identify study treatment start date. When calculating study day, the target study day will correspond to the planned study day of the nominal visit. The analysis visit values (Baseline, Day 90, Day 270, and Day 330) will be used for all presentations.

Data collected at scheduled or unscheduled visits will be used in the analysis if they fall into an analysis window for an analysis visit. If more than one visit (scheduled or unscheduled) is made within the window specified above for any analysis visit, the non-missing assessment closest to the target study day will be used in the analysis for that visit. In the case of tied visits, non-missing data from the later visit will be used. In the case of identical collection dates and times, the average of the two visits will be used. However, all data will be included in the participant data listings.

Last Visit Summaries

The protocol uses the term End of Study (EOS) for Day 330. If a participant discontinues from the study early, they will have an early termination visit that is before Day 330. Using the windowing provided in [Table 2-2](#), the early termination visit will be assigned to the nearest analysis visit. Tables that summarize data by visit will include data by analysis visit (Baseline, Day 90, Day 270, and Day 330) along with a Day 330/Last Visit which will combine data from Day 330 for those participants who have data collected within the Day 330 analysis window with the data from the last post-baseline visit for those participants who do not have data collected in the Day 330 analysis window.

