2.2 Analysis sets

The **Full Analysis Set** (FAS) comprises all randomized participants. According to the intent-to-treat principle, participants will be analyzed according to the treatment group they have been assigned to during the randomization procedure.

The **Per-Protocol Set** is a subset of the FAS in which participants are not treated with any inclsiran if they are randomized to the usual care treatment group or do not have any major protocol deviations (including deviations from inclusion/exclusion criteria) in either treatment group.

The **Restricted Set 1** is a subset of the FAS which includes only participants without changes in background lipid-lowering therapy. A change includes starting a new lipid-lowering therapy or stopping an existing lipid-lowering therapy after the study treatment start date.

The **Restricted Set 2** is a subset of the FAS which includes only participants who received three doses of inclisiran in the inclisiran + usual care group (i.e., excludes participants in the inclisiran + usual care group who missed one or more doses) and all participants in the usual care group (including participants who may have used commercially available inclisiran).

The **Safety Set** includes all participants who received study treatment. Participants will be analyzed according to the study treatment received. Refer to [Table 2-1](#) for assignment of actual treatment for the different scenarios. Participants in the usual care treatment group who have data collected at the baseline visit will be included in the Safety Set.

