2.3.1 Patient disposition

Participant disposition will be summarized as follows:

- The number of participants who signed the informed consent form, are screen failures, are randomized, are treated (Safety Set), completed the study or who discontinued early along with reasons for early study discontinuation, the number of screened subjects, completed screening phase and were randomized, completed screening phase but were not randomized, did not complete screening phase, and primary reason for not completing screening phase will be summarized for all screened participants.
- The number of participants in each analysis population will be summarized by treatment group for all randomized participants.
- The number of participants who complete the treatment phase or who discontinued treatment early along with reasons for early treatment discontinuation will be summarized for the inclisiran + usual care group for the FAS.
- The duration of exposure to inclisiran (in days) will be summarized for the inclisiran + usual care group for the FAS.
- The number of participants who complete the study or who discontinued the study early along with reasons for early study discontinuation will be summarized by treatment group for the FAS.
- The duration on study (number of days from study start date to study end date [last recorded contact/participation date in the database]) will be summarized by treatment group for the FAS.

The number and percentage of participants with important protocol deviations will be summarized by treatment group for the FAS.

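### The exposure summary can credit inclisiran days to participants who were never dosed, and defines none for usual-care participants who are counted under inclisiran for safety

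*SAP*

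**What the plan says.** SAP 2.1.1 sets the study treatment start date, labelled Day 1, at the first non-zero dose in the inclisiran + usual care group. It adds a fallback: if such a participant "does not take any study drug then treatment start date will be the randomization date". For the same group, "duration of exposure to inclisiran (in days) is defined as the number of days from Day 1" to the study treatment end date. On that end date it says "Study treatment end date is defined as the treatment phase completion date recorded on the" Treatment Disposition CRF. For the other arm, "Duration of exposure will not be defined for the usual care alone group".

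SAP 2.3.1 then states: "The duration of exposure to inclisiran (in days) will be summarized for the inclisiran + usual care group for the FAS". Under SAP 2.2 the FAS "comprises all randomized participants", analyzed as assigned.

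Table 2-1 assigns actual treatment. The inclisiran-arm row marked "Never received inclisiran" has actual treatment Usual Care. A usual-care participant with any recorded inclisiran dose, whether as study treatment or as concomitant medication, has actual treatment Inclisiran + Usual Care. SAP 2.2 analyzes the Safety Set by treatment received and points to that table.

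**The concern.** Duration of exposure tells a reader of the safety tables how long participants were observed on the drug. Two groups are handled in a way that does not fit that use.

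The first is inclisiran-arm participants with no dose. The SAP foresees them, since it gives them a fallback start date and their own row in Table 2-1, but it has no rule setting their exposure to zero or missing, or leaving them out.

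The second is usual-care participants who took inclisiran, which protocol section 3 permits. Their adverse events are shown under inclisiran with no duration alongside.

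At stake is one descriptive figure that gives context to the safety tables. No test or estimate depends on it.

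**Working it through.** The documents state no exposure figure, so there is none to reproduce. The check traces the rules for each type of participant and then shows how the mean could move.

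**Tracing the rules (SAP 2.1.1, Table 2-1, 2.2, 2.3.1)**

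| Randomized to | Inclisiran taken | In the exposure summary (FAS, as randomized)? | Exposure assigned | Safety column |
|---|---|---|---|---|
| Inclisiran + usual care | yes | yes | first dose to disposition date | Inclisiran + Usual Care |
| Inclisiran + usual care | no | yes | randomization to disposition date | Usual Care |
| Usual care | yes | no | not defined | Inclisiran + Usual Care |
| Usual care | no | no | not defined | Usual Care |

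Rows 2 and 3 are the mismatch. In row 2 the value is positive whenever the disposition date falls after randomization. It is 0 (or 1, if both end days are counted) when the two dates coincide, and cannot be computed if no date is recorded. Row 3 does not depend on any disposition date.

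**Effect of row 2 on the mean**

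Inputs: 192 participants per arm (protocol 12.8.1) and a planned treatment duration of 330 days (protocol 6.1.4). The following are assumptions, because the documents give no values: k never-dosed participants, d days assigned to each, and mean exposure E among the dosed.

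- Mean under the SAP rule: [(192 − k)E + kd]/192
- Difference from coding the never-dosed as zero: kd/192
- Difference from the mean of dosed participants only: k(d − E)/192

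With k = 5, for illustration:

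| d (days) | SAP minus zero-coded | SAP minus dosed-only, E = 330 | SAP minus dosed-only, E = 280 |
|---|---|---|---|
| 1 | 5 × 1/192 = +0.03 | 5 × (1 − 330)/192 = −8.57 | 5 × (1 − 280)/192 = −7.27 |
| 30 | 5 × 30/192 = +0.78 | 5 × (30 − 330)/192 = −7.81 | 5 × (30 − 280)/192 = −6.51 |
| 330 | 5 × 330/192 = +8.59 | 0 | 5 × (330 − 280)/192 = +1.30 |

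All entries scale with k: k = 2 gives two fifths of each and k = 10 gives double. The d = 330 row is an extreme: it needs a participant who never took a dose but whose treatment phase is recorded as running the full planned length.

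The sign depends on the comparator. Against zero-coding the SAP mean is higher or equal. Against dosed participants only, it is lower whenever d is below E. Row 3 adds a further unknown, since usual-care participants who start inclisiran late would have short durations if counted.

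**The case against.** The strongest reply is that the gap rarely matters.

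- Randomization and the first dose are scheduled at the same visit (protocol Table 8-1) and site staff give the injection (protocol 6.7.2), so never-dosed participants should be uncommon.
- Protocol 8.1.1 calls participants who fail to start treatment early terminators, which points to a disposition date near randomization, though it does not prove one.
- Protocol 4.1.1 assumes that inclisiran use in the usual care arm will be minimal.
- SAP 2.3.1 places the summary under disposition, by randomized arm, and does not call it a denominator for adverse events.
- SAP 2.4.1 separately reports doses given, missed doses and how many usual-care participants received inclisiran.
- Protocol 6.6.1 speaks of study drug exposure, so leaving commercial product out of that measure is defensible.

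All of this stands as a limit on size. None of it supplies the missing rule for a participant with no dose, and the count in SAP 2.4.1 gives no duration for those who crossed over.

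A reader might infer that reported exposure is overstated. The documents do not support that as a general statement: it holds for an individual and against zero-coding, but can reverse against the dosed-only mean. A reader might also infer that adverse event comparisons are distorted by a wrong denominator. SAP 2.7.1 plans counts, percentages and risk ratios, and no exposure-adjusted rate appears in the visible text.

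**Conclusion.** The point holds as a minor definitional defect. As written, the SAP can assign inclisiran exposure to someone it elsewhere classes as never having received the drug, and it defines none for people whose safety data it presents under inclisiran. The exposure summary is therefore misstated relative to the inclisiran safety column.

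The direction and size cannot be determined from the documents. Size depends on the number never dosed, their recorded disposition dates, and the number and timing of inclisiran starts in the usual care arm, none of which is given. It is probably small, and the never-dosed part is negligible if such participants are few and leave early but are handled consistently. No primary, secondary or planned adverse event estimate is affected.

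**What to change.** In SAP 2.1.1, start exposure at the first recorded inclisiran dose and define it only for participants with at least one dose; otherwise record it as not applicable. In SAP 2.3.1, summarize it for the Safety Set by actual treatment as in Table 2-1. Include recorded commercial inclisiran in the usual care arm or show it as a separate line, and state which end date applies to those participants, since the Treatment Disposition date is specified only for the inclisiran arm. Keep duration on study, already in SAP 2.3.1, as the FAS summary of follow-up.

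The cost is a few sentences of SAP text, one derivation and a change of analysis set for one table. Whether mean exposure rises or falls cannot be predicted: removing never-dosed participants with short assigned durations would raise it, while adding late starters from usual care could lower it.

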2.7 Safety analyses

All safety analyses will be performed on the Safety Set.

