2.7.1 Adverse events (AEs)

The Medical Dictionary for Regulatory Activities (MedDRA) dictionary will be used for coding AEs, and up-versioning will be applied during the course of study. The final MedDRA version used in this study will be v27.0. Partially missing AE dates will be imputed following Appendix 5.1.2. An AE (classified as preferred term) occurring during the treatment period will be counted as a treatment-emergent AE (TEAE) either if it is not present at Day 1 before treatment or if it is present before treatment but increased in severity during the treatment period. Therefore, all recorded AEs with onset on or after the study treatment start date will be counted as TEAE. In case the AE date values do not allow unequivocally allocating an AE record to TEAE or non-TEAE, the AE will be considered as TEAE in the statistical analysis. The following summary tables will be presented:

- Overall Summary of TEAEs
- TEAEs by System Organ Class (SOC) and Preferred Term (PT)
- TEAEs by PT
- Common ($\geq 3\%$ within either treatment group) by PT
- TEAEs by SOC, PT, and Severity
- TEAEs by SOC, PT, and Relationship to Study Treatment
- Related TEAEs by SOC, PT, and Severity
- Treatment Emergent Serious AEs (TESAEs) by SOC and PT
- TESAEs by PT
- TESAEs by SOC, PT, and Severity
- TESAEs by SOC, PT, and Relationship to Study Treatment
- Related TESAEs by SOC, PT, and Severity
- TEAEs Leading to Withdrawal of Study Treatment by SOC and PT
- TEAEs with a Fatal Outcome by SOC and PT

If more than one event occurred with the same PT for the same participant, the participant will be counted only once for that PT using the most severe or related occurrence for the summary by severity, or relationship to study drug, respectively.

Missing severity and relationship will not be imputed and will be identified as 'missing' in the tables.

For common (3% within either treatment group) TEAEs, serious TEAEs and TEAEs leading to withdrawal of study treatment, risk ratios along with 95% confidence intervals will be presented to compare treatment groups with respect to risk.

For tables presented by SOC and PT, system organ classes are sorted alphabetically and within each system organ class, the preferred terms are sorted in descending order of total frequency.

For tables presented by PT, preferred terms are sorted in descending order of total frequency.

Listings will be presented for participants with SAEs and AEs leading to discontinuation of study treatment.

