2.7.3 Laboratory data

Laboratory values will be summarized by treatment group, including the observed value, changes and percent changes from baseline at each analysis visit (including Day 330/Last Visit).

Estimated glomerular filtration rate (eGFR) in mL/min/1.73m² will be derived using the Modification of Diet in Renal Disease approach according to the following formula based on serum creatinine values in mg/dL (Levey et al. 2006):

$$\text{eGFR} = 175 \times \text{Serum Cr}^{-1.154} \times \text{Age}^{-0.203} \times 1.212 \text{ (if participant is black)} \times 0.742 \text{ (if female).}$$

Fasting glucose parameter, when used in any analysis, will require the lab sample to be taken while fasting. Glucose values recorded under non-fasting conditions will not be used. For all safety analyses, baseline fasting glucose uses the **average of the last two assessments** measured under fasting conditions at or prior to baseline. If only one fasting glucose value is available at or prior to baseline, the analysis will be based on the available data.

A shift analysis using the normal range (except for eGFR and HbA1c) will be done which counts the number of participants with a low, normal or high value at baseline and a low, normal or high value post baseline.

The following ranges will be used for eGFR and hemoglobin A1c (HbA1c):

- For eGFR, the categories will be Severe = <30 mL/min/1.73m²; Moderate = ≥ 30 to <60 mL/min/1.73m²; Mild = ≥ 60 to <90 mL/min/1.73m²; and Normal = ≥90 mL/min/1.73m².
- For HbA1c, the categories will be ≤5.6%, ≥5.7% to ≤6.4%, and ≥6.5%.

The baseline and worst post-baseline value will be utilized for the shift tables. Note that the shift table dealing with the fasting glucose parameter will require the lab sample to be taken while fasting. Samples taken while the participant was not fasting will not be analyzed. For CSR purposes, HbA1c will be reported under clinical chemistry, not hematology.

New onset or worsening of diabetes during the study will be identified by evaluating different components: 1) adverse events, 2) laboratory measures of either fasting glucose or glycated hemoglobin (HbA1c) and 3) initiation of antidiabetic medication. New onset or worsening of diabetes is defined if ANY of the following conditions are met post-baseline:

- Laboratory results indicating diabetes, which can be any of the following:
 - The participant has HbA1c ≥6.5% on two consecutive tests.

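### SAP Table 2-1 counts usual-care participants who later receive inclisiran under inclisiran from randomization, so pre-dose safety events are attributed to the drug; the departure from protocol 12.1 is undeclared

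*SAP*

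**What the plan says.** SAP 2.1.1, Table 2-1, separates planned from actual treatment. In its third row, a participant randomized to Usual Care who "Received at least one dose of inclisiran" keeps Usual Care as planned treatment but has Inclisiran + Usual Care as actual treatment. The column header defines the trigger as "Inclisiran Use Recorded as Study Treatment or Concomitant Medication", so commercial inclisiran prescribed by the treating physician is enough.

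SAP 2.2 refers the Safety Set to that table "for assignment of actual treatment for the different scenarios", and SAP 2.7 adds: "All safety analyses will be performed on the Safety Set".

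The study treatment start date (Day 1) is the "first date when a non-zero dose of study drug is administered for the inclisiran + usual care group". The SAP also states: "For the usual care alone group the study treatment start date will be the randomization date". Under SAP 2.7.1, "all recorded AEs with onset on or after the study treatment start date will be counted as TEAE". Under SAP 2.7.3, "The baseline and worst post-baseline value will be utilized for the shift tables".

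Protocol 12.1 defines treatment received for the Safety Set differently. It is the assigned treatment if the participant took at least one dose of it; if the assigned treatment was never received, it is the first treatment received.

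SAP section 4 lists seven changes from the protocol. None concerns treatment received in the Safety Set.

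**The concern.** Protocol section 3 allows commercial inclisiran in the usual-care arm, so the third row covers a situation that the design permits. The row changes the participant's column for the whole study, while the date from which events count stays at randomization. No rule sets a new start date or baseline at the first inclisiran dose.

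The outputs affected are the between-group risk ratios for common TEAEs, serious TEAEs and TEAEs leading to withdrawal of study treatment, and the chemistry shift, clinically significant value and Hy's Law tables. Their inclisiran column could hold events and values from before any exposure. Overall safety and tolerability of inclisiran is a stated secondary objective, so attribution in that column matters. Duration of exposure (SAP 2.3.1) is summarized only for the inclisiran + usual care group on the FAS and is not defined for usual care alone. Crossovers would therefore join the safety column without contributing to the exposure-duration summary.

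**Working it through.** **Following the rules for one participant.** Take someone randomized to usual care who has an SAE in month 2 and a first commercial dose in month 7.

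| Step | Source | Result |
|---|---|---|
| Column | SAP Table 2-1, third row; SAP 2.2 | Inclisiran + Usual Care |
| Day 1 | SAP 2.1.1 | Randomization. The first-dose rule needs study drug, and its fallback covers only those randomized to inclisiran |
| Month 2 SAE | SAP 2.7.1 | TEAE, because onset is after Day 1 |
| Laboratory values, months 1 to 6 | SAP 2.1.1, 2.7.3 | Post-baseline, so eligible as the worst value |
| Column under the protocol | Protocol 12.1 | Usual Care: assigned, and received first |

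**Chemistry.** Protocol Table 8-1 schedules post-baseline chemistry at Days 90, 270 and 330. The scheduled samples that precede inclisiran are 0 of 3 for crossover before the Day 90 visit, 1 of 3 between the Day 90 and Day 270 visits, and 2 of 3 after Day 270. Post-baseline hematology is scheduled only at Day 330, so it is largely unaffected.

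**Size.** The plan states no crossover figure to reproduce. Its arm size does reproduce: the stated inputs (difference 15, SD 40, two-sided 0.025, power 0.85) give 153 per arm, and 153/0.8 = 191.25, rounded up to 192.

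The rest are assumptions: k = 4, 10 or 19 crossovers (about 2%, 5% and 10% of 192), first inclisiran at Day 165 on average, and a 20% SAE risk over 330 days with constant hazard.

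- Pre-dose share of the inclisiran column's person-time = k × 165 / [(192 + k) × 330]
- Participants with a pre-dose SAE = k × (1 − 0.8^(165/330)) = k × 0.1056
- SAE participants in the column = 0.2 × (192 + k)

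| k | Person-time share | Pre-dose SAE participants | Column SAE participants | Share of those |
|---|---|---|---|---|
| 4 | 660/64,680 = 1.0% | 0.42 | 39.2 | 1.1% |
| 10 | 1,650/66,660 = 2.5% | 1.06 | 40.4 | 2.6% |
| 19 | 3,135/69,630 = 4.5% | 2.01 | 42.2 | 4.8% |

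With crossover at Day 60 the factor is 1 − 0.8^(60/330) = 0.0398, giving 0.2, 0.4 and 0.8 participants. At Day 280 it is 1 − 0.8^(280/330) = 0.1725, giving 0.7, 1.7 and 3.3.

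The column percentage is 39.2/196 = 40.4/202 = 42.2/211 = 20.0%, the same as 38.4/192 without crossovers.

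**The case against.** **Extent is reported.** SAP 2.4.1 plans to summarize how many participants randomized to usual care received inclisiran. A reader might infer that crossovers would go unnoticed; they would not. Adverse event and concomitant medication listings should also let much of the timing be recovered. This stands, but no planned table splits events at first dose, and SAP section 4 limits laboratory listings to abnormal data.

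**The protocol sentence fits usual care loosely.** Usual care has no protocol-defined dose. Protocol 6.1 names only inclisiran as the study treatment provided, and 9.1.1 applies treatment discontinuation only to the inclisiran group. Table 2-1 could be seen as making an awkward sentence workable. Against that, the protocol summary lists usual care alone as a study treatment, and a crossover received it first. Usual Care is the natural reading, though not a perfectly worded one.

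**As-treated grouping has a rationale.** It keeps post-inclisiran injection-site and hypersensitivity events with the drug. That supports counting events after the dose, not those before it.

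**Two stronger readings.** A reader might infer that the risk ratios are biased against inclisiran. They would be if events prompted crossover: with 5% event risk, 5% crossover without an event and 10%, 20% or 30% after one, a null risk ratio becomes 1.10, 1.34 or 1.64. Nothing in the documents supports those crossover probabilities. Also, a participant must survive to cross over, so fatal events cannot precede the dose. The direction is unknown. A reader might also infer that commercial-only users have no Day 1, by taking the start-date rule to mean the actual group. The next sentence's reference to randomization makes that implausible; the point deserves a clarifying sentence, nothing more.

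**Conclusion.** The rule is wrong as written and small in likely effect. Applied exactly, the SAP tabulates events and laboratory values from before any inclisiran under inclisiran, contrary to the natural reading of protocol 12.1 and without declaring the change. Protocol 4.1.1 expects crossover to be minimal and gives no number. The estimate of about 0.4 to 2.0 participants rests on the assumed crossover rate, timing and SAE risk; the timing range tried widens it to 0.2 to 3.3. If crossovers have the background rate, the problem is attribution of events, not a shift in the rate. Primary and secondary efficacy analyses on the FAS use randomized groups and are unaffected.

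**What to change.** Before database lock:

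1. Set actual treatment in the third row of Table 2-1 to Usual Care for the comparative safety tables, consistent with protocol 12.1.
2. State that Day 1 for every participant randomized to usual care is the randomization date.
3. Add a table or listing of crossovers' adverse events and notable laboratory values with onset on or after first inclisiran. Show first-dose dates and flag imputed ones, because rule (B) in SAP 5.1.2 can place a partial medication start date at treatment start.

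The cost is one table row, one sentence and one small output. The downside is that a few post-inclisiran events, possibly injection-site or hypersensitivity events, sit in the usual-care column; the added output shows them.

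If the sponsor prefers as-treated grouping, declare it in SAP section 4 and add the same safety tables by randomized arm. Flag crossovers' events from before first inclisiran and do not count them as inclisiran TEAEs. This costs more programming and also needs a first-inclisiran date for each crossover.
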